#### 2.1.3.3 Other Secondary Objectives

The other efficacy secondary objectives of this study are

- To compare efficacy of plitidepsin 1.5 mg or 2.5 mg versus the control in terms of hospital readmission related to COVID-19.
- To compare efficacy of plitidepsin 1.5 mg or 2.5 mg versus the control in terms of clinical evolution.
- To compare efficacy of plitidepsin 1.5 mg or 2.5 mg versus the control in terms of the need of supplementary oxygen.
- To compare efficacy of plitidepsin 1.5 mg or 2.5 mg versus the control in terms of the need of intensification of respiratory or intensive care support.
- To compare efficacy of plitidepsin 1.5 mg or 2.5 mg versus the control in terms of the need of intensification of pharmacological therapies.
- To compare efficacy of plitidepsin 1.5 mg or 2.5 mg versus the control in terms of superinfections.
- To compare efficacy of plitidepsin 1.5 mg or 2.5 mg versus the control in terms of mortality.
- To compare efficacy of plitidepsin 1.5 mg or 2.5 mg versus the control in terms of the evolution of viral load.
- To compare efficacy of plitidepsin 1.5 mg or 2.5 mg versus the control in terms of the evolution of inflammatory markers.
- To compare efficacy of plitidepsin 1.5 mg or 2.5 mg versus the control in terms of the immune response against severe acute respiratory syndrome coronavirus 2 (SARS-CoV-2).
- To compare efficacy in the primary endpoint and describe safety/tolerability of pooled plitidepsin arms versus control.
- To compare efficacy in the primary endpoint and describe safety/tolerability between plitidepsin arms (1.5 versus 2.5 mg) in case both are significantly superior to the control.
- To explore the influence of risk factors or scores for clinical deterioration that were not individually included.
- To compare the results obtained before and after the change of the primary and key secondary endpoint (protocol v.6 versus v.7).

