## 2.3 Sample Size and Power

A total sample size of 609 patients (203 in each arm) with 530 events necessary for the analysis of the primary endpoint has been calculated based on a 1-sided type I error rate of 1.25% ( $\alpha = 0.0125$ ) with at least 80% power ( $\beta = 0.2$ ) to detect target hazard ratio (HR) of 1.4 in the time to sustained withdrawal of supplementary oxygen, which means a decrease in the median time to the event from 8 days (control arm) to 5.7 days (plitidepsin). This sample size is adjusted for the multiple comparisons of each plitidepsin arm with control group by a Bonferroni adjustment, although other advanced methods for correction of multiplicity will be used for the main analysis that will increase the power of the tests. At the final analysis, if HR is 1.27 or greater, in favour of any plitidepsin arm, (equivalent to a decrease in the median time to sustained withdrawal of supplementary oxygen of 1.7 days or greater), then it is expected that the null hypothesis (ie, HR  $\leq$ 1) will be rejected.

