A subgroup analysis has been defined to assess this endpoint (see Section 7.6.4).

 Time to sustained withdrawal of supplementary oxygen (11-category WHO Clinical Progression Scale ≤4) with no subsequent reutilisation during remaining study period, before (protocol v.6) and after the amendment (protocol v.7). A subgroup analysis has been defined to assess this endpoint (see Section 7.6.4).

• Time to sustained (ie, with no subsequent readmission to Day 31) hospital discharge (since randomisation), before (protocol v.6) and after the amendment (protocol v.7)

A subgroup analysis has been defined to assess this endpoint (see Section 7.6.4).

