### 7.6.4 Subgroup Analysis

The primary and key secondary efficacy endpoint will be analysed using the ITT population by the following subgroups:

- Charlson Comorbidity index (as derived using the eCRF data): 0 1' or > 1'
- Geographical Region: Europe or Rest of the World
- Pre-baseline Barthel index:  $\geq 90'$  or  $\leq 90'$
- Patients included before and after amendment: 'Protocol v.6 or before' or 'Protocol v.7'

The same covariates used for the primary efficacy endpoint analysis will be used for the subgroup analyses except that for the Charlson Comorbidity index subgroup analysis, the randomisation stratum of Charlson Comorbidity index will not be included as a covariate; for the Geographical Region subgroup analysis, the randomisation stratum of Geographical Region will not be included as a covariate; and for the pre-baseline Barthel index subgroup analysis, the randomisation stratum of pre-baseline Barthel index will not be included as a covariate.

Additionally, the primary efficacy endpoint will be analysed by the following subgroups:

- Sex: female or male
- Age at study entry: '18 to 39', '40 to 64' or ' $\geq$  65 years'
- Race: Asian, black, white or other
- Ethnic group: 'Hispanic or Latino' or 'Not Hispanic or Latino'

- Site location: each study site with more than 1/6 out of the randomised patients (ie, >33 randomised patients for the futility analysis and >101 randomised patients for the final analysis) will be considered as a group and the remaining study sites, ie, those study sites with less than 1/6 out of the randomised patients will be pooled together as a one single group.
- Use of antiviral therapies or immunomodulatory drugs through the study: Yes or No
- Previous COVID-19 vaccination status: 'Fully vaccinated', 'Non-fully vaccinated', 'No vaccinated', or 'Fully vaccinated + Non-fully vaccinated'
- Anti-SARS-CoV-2 IgG at Day 1: 'Non-positive' or 'Positive'
- Pre-randomisation dexamethasone: Yes or No
- Total duration of corticoid therapy: `< 9 days', `[9 11] days' or `> 11 days'
- Total cumulative dose of corticoid therapy (dexamethasone or equivalent): `≤ 60 mg' or `> 60 mg'
- SARS-CoV-2 viral load (log10 copies/mL) at Day 1 before study drug administration: '< 4', `[4 - 7]' or `> 7'
- Time between onset date of COVID-19 symptoms and initiation of study treatment: `≤ 5 days', `6 - 10 days' or `> 10 days'
- Body mass index (kg/m^2) at Screening: < 30 or  $\geq$  30 (Obesity)

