- Hypertension at Screening, defined as Hypertension (Standardised MedDRA Query [SMQ]) in the Medical History form: Yes or No
- Individual co-morbidities included in the Charlson Index: myocardial infarction (Yes or No), congestive heart failure (Yes or No), peripheral vascular disease (Yes or No), cerebrovascular disease (Yes or No), dementia (Yes or No), chronic obstructive pulmonary disease (Yes or No), connective tissue disease (Yes or No), peptic ulcer disease (Yes or No), liver disease ('None', 'Mild' or 'Moderate or Severe'), diabetes mellitus ('None or diet controlled', 'Uncomplicated' or 'End-organ damage'), hemiplegia (Yes or No), moderate or severe chronic kidney disease (Yes or No), solid tumor ('None', 'Localized' or 'Metastatic'), leukemia (Yes or No), lymphoma (Yes or No) or AIDS (Yes or No).
- ISARIC-4C mortality score: Low (0 3), Intermediate (4 8), High (9 14) or Very high (≥ 15)
- ISARIC-4C deterioration probability (%): `≤ 25', `(25 50]', or `> 50'
- Lactate dehydrogenase (LDH) at Baseline: ≤ ULN or > ULN

- CRP (mg/L) at Baseline: ≤ 100 or > 100
- D-dimer at Baseline: ≤ ULN or > ULN
- Ferritin at Baseline: ≤ ULN or > ULN
- Creatinine at Baseline: ≤ ULN or > ULN
- IL-6 at Baseline: ≤ Median or > Median value (at the analysis time cutoff may be updated based on distribution values if needed)
- IL-10 at Baseline: ≤ Median or > Median value (at the analysis time cutoff may be updated based on distribution values if needed)
- Lymphocytes count decreased at Baseline: 'Grade 0' or 'Grade  $\geq 1'$
- Neutrophils/lymphocytes ratio at Baseline:  $< 6 \text{ or } \ge 6$
- SARS-CoV-2 variant: Alpha, Beta, Gamma, Delta, Eta, Iota, Kappa, Lambda, Mu, or any potential new variant

The same covariates used for the primary efficacy endpoint analysis will be used for the subgroup analyses.

For ISARIC-4C mortality score and deterioration probability calculation:

- A Glasgow coma scale score of 15 is assumed for all the patients.
- Urea (mmol/L) will be calculated as blood urea nitrogen (mmol/L) \* 60 / 28.

Forest plots of the hazard ratios, and the 95% CI for the comparison of each dose of plitidepsin versus control arm will be presented by endpoint for all subgroups using the ITT population.

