#### 7.6.5 Exploratory Analysis

A multivariate analysis will be performed for the primary and key secondary efficacy endpoint, including the treatment group, randomisation stratification factors and all the above subgroup variables as covariates. Those covariates with more than 10% of missing values will be omitted from the multivariate analysis. A stepwise selection model will be used, with significant level equal to 0.2 and 0.05, to enter into the model and to remain in the model, respectively.Treatment group will be forced to be included in addition to the significant covariates.

Time-to sustained withdrawal of oxygen supplementation will be compared between each dose of plitidepsin versus control arm receiving the antiviral control arm, ie, the regulatory-approved antiviral for those patients randomised to the control arm (remdesivir or favipiravir).

Time-to sustained withdrawal of oxygen supplementation will be analysed using the Kaplan-Meier method and 25th percentile, median and 75th percentile time will be presented for the plitidepsin arms and control arm receiving the antiviral control

Sponsor Name: Pharma Mar S.A. Sponsor Protocol ID: APL-D-003-20

arm, together with 95% CIs. The 95% CIs will be computed based on Brookmeyer-Crowley method and using a log log transformation. The mean time to sustained withdrawal of oxygen supplementation and its standard error will be also presented for the pooled plitidepsin arms and control arm.

Time-to sustained withdrawal of oxygen supplementation between each dose of plitidepsin versus control arm receiving the antiviral control arm will be compared using a stratified log-rank test, including the randomisation stratification factors as covariates, ie, Geographical Region (Europe vs. Rest of the World), Charlson Comorbidity index (0-1 vs. >1) and pre-baseline Barthel index ( $\geq$ 90 versus <90) as derived using the eCRF data. The 2-sided p-values for the comparison of the pooled plitidepsin arms versus control arm will be presented.

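### Comparing results before and after the amendment is a stated objective, but the SAP plans only a separate hazard ratio in each period and no estimate of how the treatment effect differs between them

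*SAP*

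**What the plan says.** The last objective in SAP section 2.1.3.3 is "To compare the results obtained before and after the change of the primary and key secondary endpoint (protocol v.6 versus v.7"). Section 3.5 lists the matching endpoints: time to sustained oxygen withdrawal and time to sustained discharge, each before and after the amendment. Section 7.6.2.3 gives both the same one-line method: "A subgroup analysis has been defined to assess this endpoint (see Section 7.6.4").

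Section 7.6.4 opens with "The primary and key secondary efficacy endpoint will be analysed using the ITT population by the following subgroups" and includes the factor "Patients included before and after amendment: 'Protocol v.6 or before' or 'Protocol v.7". On the model it states: "The same covariates used for the primary efficacy endpoint analysis will be used for the subgroup analyses", with each stratification factor dropped for its own subgroup analysis. The output is "Forest plots of the hazard ratios, and the 95% CI for the comparison of each dose of plitidepsin versus control arm". The shells for Figures 14.2.1.2 and 14.2.2.2 show patient numbers, HR (95% CI) and the plot. Their model footnotes name treatment and the stratification factors only. The addendum's reissued forest plot (Figure 14.2.1.2.1) adds no contrast between periods.

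The multivariate model in section 7.6.5 is described as "including the treatment group, randomisation stratification factors and all the above subgroup variables as covariates", so period can enter there only as a main effect.

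**The concern.** Each within-period HR addresses whether plitidepsin differs from control in that period. The objective asks something else: whether the treatment effect is the same in the two periods. A main effect of period does not answer this either. It describes whether patients came off oxygen faster in one period, whatever their arm.

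The trial is open-label and the amendment changed the primary and key secondary endpoints, so consistency across it bears on credibility. With two intervals side by side, a reader is likely to note which one excludes 1. That comparison produces apparent inconsistency when the effects are equal, and it never states how large a change between periods the data can rule out.

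**Working it through.** **Inputs from the SAP.** Section 2.3: target HR 1.4, "1-sided type I error rate of 1.25"%, at least 80% power, 530 events over three arms, 353 in a two-arm comparison, 116 per pair at the 33% look. Section 7.1: other tests two-sided at 0.05. Section 8: recruitment stopped before 33% of events and the futility analysis was cancelled.

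**Assumptions.** The final event count is not given. 33% of 530 is 174.9, and two thirds of 175 is about 117 per pair, so 116 is taken as the approximate ceiling and 80 as a lower case. The split of events between periods is not given either; 50:50 to 80:20 is shown. Allocation is 1:1, so the variance of a log HR is about 4/events. The periods contain different patients, so their estimates are independent.

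**The plan's own figures first.**
- Critical HR at 353 events: exp(2.2414 × 2/√353) = 1.269; the SAP says 1.27.
- Power at 353 events: 82.1%; the SAP says at least 80%.
- Z at 116 events and HR 1.4: ln(1.4) × √116/2 = 1.812; the SAP says 1.812.

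The approximation reproduces the design.

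**Discordant significance when the effects are equal.** Power in a period with d events is P(|N(m,1)| > 1.96), with m = ln(HR) × √d/2. The chance that exactly one period is significant is p₁(1−p₂) + p₂(1−p₁).

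Example with 116 events split 58/58 and HR 1.4: m = 0.3365 × 7.616/2 = 1.281, power 0.249 in each period, discordance 2 × 0.249 × 0.751 = 37.4%.

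| True HR in both periods | Events per pair | 50:50 | 70:30 | 80:20 |
|---|---|---|---|---|
| 1.4 | 116 | 37.4% | 38.6% | 40.1% |
| 1.4 | 100 | 34.5% | 35.4% | 36.6% |
| 1.4 | 80 | 30.3% | 31.0% | 31.8% |
| 1.27 | 116 | 25.4% | 25.7% | 26.2% |
| 1.2 | 116 | 19.1% | 19.2% | 19.4% |
| 1.0 | any | 9.5% | 9.5% | 9.5% |

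A larger true effect gives more: at HR 1.6 and 116 events, 49–57%. A two-sided 5% interaction test signals in 5% when the effects are equal.

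**What the direct contrast could deliver.** SE of the log ratio of HRs = √(4/d₁ + 4/d₂).
- 116 events, 58/58: SE = √(8/58) = 0.371. The 95% CI is the estimate times or divided by exp(1.96 × 0.371) ≈ 2.1. An estimated ratio of 1 would carry an interval of about 0.48 to 2.07.
- Power for a true ratio of 1.4 at 116 events: 14.6% (50:50), 12.9% (70:30), 10.8% (80:20).
- Ratio detectable with 80% power at 116 events: 2.83 (50:50), 3.11 (70:30).

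**The case against.** **The SAP never says that consistency is to be read from which interval excludes 1.** True. The discordance rate describes a likely reading, not a planned rule. The forest plot prints the HR and CI for each period, and because the periods contain different patients, a reader could derive an approximate ratio of HRs. So the information is not withheld. It remains the case that the plan itself does not produce the estimate its objective needs.

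**The objective may be descriptive.** It is the last of many other secondary objectives, no test is promised, and the section 3.5 endpoints are delivered per period. Section 7.6.2.3 also answers an objective to compare the two doses by stating that no statistical comparison between them will be made. That shows the verb can be used loosely here, but also that the authors said so when they meant it. No such statement covers the amendment.

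**Other analyses touch the same worry.** Section 8 plans an exploratory analysis of the former v.6 primary endpoint at the final analysis. That helps with the change of endpoint, but it does not compare the treatment effect between periods.

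**An interaction test would be weak.** This stands: power is 13–15% for a ratio of 1.4 at 116 events with splits of 50:50 to 70:30. A non-significant result would not show consistency, so the estimate and its interval should carry the answer.

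**A reader might infer that equal effects will look different about half the time.** Rates of 48–55% arise at HR 1.4 with 353 events per pair and splits of 50:50 to 70:30. That is the full design, which section 8 shows was abandoned. No single rate holds without stating the HR, the event count and the split.

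**Conclusion.** The concern holds in a limited form. A stated comparison between periods has no planned comparative estimate anywhere in the SAP, the shells or the addendum. That follows from the text and needs no assumption.

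The size is conditional. About 30–40% discordant significance requires a true HR of 1.4 in both periods, 80–116 events per pair, an assumed split of 50:50 to 80:20, and a reader who judges by which 95% CI excludes 1. With smaller effects the rate is lower, down to 9.5% when the HR is 1. The documents do not support an unconditional error rate, nor a claim that an interaction test would settle the question at this trial's size. They also do not support extending the criticism to every subgroup factor, since only the amendment comparison rests on this objective. The primary analysis is unaffected.

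**What to change.** In section 7.6.4, for each dose and for the primary and key secondary endpoints, fit one stratified Cox model on all ITT patients with period and treatment-by-period added. Report the ratio of HRs (v.7 over v.6 or before) with its 95% CI as the answer to this objective, and the interaction p-value as exploratory. Keep the separate HRs as description. State the low precision next to the result, using the actual events in each period.

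Restrict this to the amendment factor. Section 7.6.4 lists 46 other factors; with two doses that is 92 tests and 92 × 0.05 = 4.6 expected false signals on the primary endpoint. The vaccination levels also overlap, so no single interaction term fits them as listed.

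The cost is a paragraph of SAP text, one model per dose and endpoint, and one small table or figure row. No new data are needed. The addendum puts database lock at 26 April 2023, so anything added after that must be labelled post hoc; a further addendum of the same kind could carry it.

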### 7.6.3 Sensitivity Analysis

As a sensitivity analysis for the primary efficacy endpoint:

- For the Cox regression model of the primary efficacy endpoint, the proportional hazard assumption will be checked by means of a Cox regression including treatment and its time dependent covariate, i.e., treatment group\*log(time). Censored patients at time 0 will not be used in the model. In case of strong rejection of proportionality, ie, p-value < 0.05, then restricted mean survival estimates will be calculated at Days 4, 8, 15, and 31 and weighted log-rank tests (if applicable) will also be calculated in addition to the hazard ratios from the stratified Cox regression model.
- Time-to sustained withdrawal of oxygen supplementation between each dose of plitidepsin versus control arm will be compared on the FAS population.
- Time-to sustained withdrawal of oxygen supplementation between each dose of plitidepsin versus control arm will be compared using an unstratified logrank test and Cox regression model on the ITT population. The hazard ratios, 95% CIs, and 2-sided p-values for the comparison of each dose of plitidepsin versus control arm will be presented.
- If at least the 5% of the patients in any treatment group are mis-stratified then the time-to sustained withdrawal of oxygen supplementation between each dose of plitidepsin versus control arm will be compared using a stratified log-rank test and Cox regression model on the ITT population. The model will be adjusted for the randomisation stratification factors as they were collected in IRT, ie, Geographical Region (Europe vs. Rest of the World), Charlson Comorbidity index (0-1 vs. 2 or Greater) and Barthel index (≥90 versus <90) as collected in IRT. The hazard ratios, 95% CIs, and 2-sided p-values for the comparison of each dose of plitidepsin versus control arm will be presented.

Moreover, as a sensitivity analysis for the key secondary efficacy endpoint:

• Time-to sustained hospital discharge between each dose of plitidepsin versus control arm will be compared on the FAS population.

 Time-to sustained hospital discharge between each dose of plitidepsin versus control arm will be compared using an unstratified log-rank test and Cox regression model on the ITT population. The hazard ratios, 95% CIs, and 2-sided p-values for the comparison of each dose of plitidepsin versus control arm will be presented.

As a sensitivity analysis for the other time-to-event secondary efficacy endpoints, eg, time to initiation with immune-modulating or antiviral drugs, overall survival, and time to intensification of respiratory support:

- Each dose of plitidepsin versus control arm will be compared on the FAS population.
- Each dose of plitidepsin versus control arm will be compared using an unstratified log-rank test and Cox regression model on the ITT population. The hazard ratios, 95% CIs, and 2-sided p-values for the comparison of each dose of plitidepsin versus control arm will be presented.

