# 8. Changes in Planned Analysis

Despite wording in Protocol that WHO score 0 requires a test with RNA undetected (which would be achieved with a PCR or similar test), as scarce cases have been reported, Pharma Mar is accepting negative antigen tests (which is a protein detection test, and not RNA detection test) qualifying for score of 0.

Recruitment was stopped due to slow recruitment before reaching the 33% of events by Pharma Mar decision and futility analysis was cancelled.

An exploratory analysis of the comparison of the primary efficacy endpoint between each dose of plitidepsin versus control arm receiving and not receiving the antiviral control arm, ie, the regulatory-approved antiviral for those patients randomised to the control arm (remdesivir or favipiravir), will be performed.

CONFIDENTIAL

An exploratory analysis of the prior primary efficacy endpoint based on protocol amendment v6 will be performed at the final analysis time due to some regulatory agencies request.

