• If time dependent covariate p-value is <0.05 then restricted mean survival at Day 4, Day 8, Day 15 and Day 31 will be calculated. Otherwise, restricted mean survival at Day 4, Day 8, Day 15 and Day 31 will not be calculated and their rows will be removed from the table.

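### Restricted mean times for the primary endpoint appear only if a low-powered proportional-hazards test gives p < 0.05; otherwise the hazard ratio is the only between-arm effect estimate

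*SAP*

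**What the plan says.** Section 7.6.3 fits a Cox model with treatment and treatment multiplied by log(time). The consequence is conditional: "In case of strong rejection of proportionality, ie, p-value < 0.05, then restricted mean survival estimates will be calculated". The time points named for this are Days 4, 8, 15 and 31. Weighted log-rank tests, where applicable, fall under the same condition. Both would come on top of the stratified Cox hazard ratios and replace nothing.

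The programming notes to Table 14.2.1.1.2 give the other branch. If the p-value is not below 0.05, the restricted means "will not be calculated and their rows will be removed from the table". The shell has one p-value cell covering all three arms. Its restricted-mean rows give one value per arm, with no difference between arms and no confidence interval. It has no row for the weighted log-rank tests, and their weights are not named.

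Section 8 sets the context: "Recruitment was stopped due to slow recruitment before reaching the 33% of events by Pharma Mar decision and futility analysis was cancelled".

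**The concern.** A test of proportional hazards that does not reject says little when the test has low power. Here the non-rejection has a consequence: the alternative between-arm analyses are not produced. The hazard ratio, in its stratified, unstratified and bootstrap versions, is then the only estimate comparing arms on the primary time-to-event endpoint.

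A time-varying effect is plausible. Plitidepsin is given on Days 1 to 3 (Section 2.2) and the endpoint runs to about Day 31. If the hazard ratio changes over that period, a single Cox estimate is an average that depends on follow-up. A reader would have no estimate, with its uncertainty, of how many days of oxygen a dose saves. Whether such an estimate could appear at all depends on a pretest run on the same data.

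**Working it through.** **1. Reproducing the plan's figures (Section 2.3).** The plan states "A total sample size of 609 patients (203 in each arm) with 530 events necessary for the analysis of the primary endpoint", with "with at least 80% power" "to detect target hazard ratio (HR) of 1.4 in the time to sustained withdrawal of supplementary oxygen", one-sided alpha 0.0125 and 1:1:1 allocation.

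- Schoenfeld events per pair: 4(2.241 + 0.842)² / (ln 1.4)² = 336.
- The plan uses 353 per pair. Power is Φ(0.3365 × √353/2 − 2.241) = 82.1%, falling to 80.1% once the futility stop is applied. Three arms: 353 × 1.5 = 529.5, i.e. 530.
- Critical HR: exp(2 × 2.241/√353) = 1.27, as stated.
- Interim Z at 116 events: 0.3365 × √116/2 = 1.812, as stated.

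The sizing is sound. It concerns the log-rank comparison; the SAP gives no power for the proportionality test.

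**2. Events available.** 33% of 530 is 175, and 33% of 353 is about 116 per pair. Section 8 says only that recruitment stopped before that point. Patients already enrolled could still have events, so I used about 110-143 per pair as an assumption.

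**3. What the test can detect at 116 events per pair.** The simulated standard error of the log(time) slope is about 0.205. Power of 80% needs a slope of (1.96 + 0.84) × 0.205 = 0.57. Between Day 2 and Day 15 that is exp(0.57 × ln 7.5), about a 3.2-fold change in the hazard ratio.

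**4. Miss rates.** Assumptions: exponential control arm with the plan's median of 8 days, whole-day times, censoring at Day 31, one dose against control, unstratified, two-sided 0.05. The patterns are mine; the SAP gives none. With 1,500 replicates, Breslow ties, and the crossing placed at Day 4:

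| Assumed hazard ratio | ~110 events | ~128 | ~143 | 203 per arm |
|---|---|---|---|---|
| 1.0 to Day 4, then 1.7 | 83% | 81% | 78% | 56% |
| 1.8 to Day 5, then 1.0 | 80% | 78% | 76% | 39% |
| 0.8, then 1.6 | 77% | 73% | 69% | 32% |

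Rejection under a constant HR was 3-4%. Further runs gave 78-85% at about 110 events and 70-82% at about 143. The last column flatters the test: with censoring only at Day 31, 203 per arm yields about 388 events per pair under HR 1.4, against the planned 353.

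**5. Other patterns, about 116 events per pair (Efron ties).**

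| Assumed hazard ratio | Missed |
|---|---|
| 1.8 to Day 8, then 1.0 | 80% |
| 2.0 to Day 8, then 1.0 | 74% |
| 2.0 to Day 4, then 1.0 | 67% |
| 1.0 to Day 4, then 1.6 | 83% |
| 1.0 to Day 4, then 2.0 | 70% |
| 1.0 to Day 8, then 2.0 | 68% |

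A two-degree-of-freedom test over three arms, closer to the single p-value in the shell, gives 67-85% for these six.

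Over about 95-143 events per pair, strong crossing (1.8 then 0.6, or 0.7 then 2.0) is missed about 40-57% of the time. Mild drift (1.6 to Day 5, then 1.2) is missed 89-93% of the time.

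**The case against.** Several stronger readings are tempting, and the documents do not support them.

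- A reader might infer that the SAP takes p ≥ 0.05 as proof of proportional hazards. It never says so; it only makes further analyses conditional. What stands is that it acts on the result by dropping them.
- A reader might infer that only the hazard ratio is left. Section 7.6.1 always gives, per arm, the Kaplan-Meier quartiles in days with 95% CIs, the mean with its standard error, and the curves. With censoring by about Day 31 that mean is in effect a restricted mean. But no truncation time is stated and no between-arm contrast is given.
- Section 7.6.2.3 does give between-arm differences with exact CIs in the percentage needing oxygen on Days 4, 8, 15 and 31. Those are free of proportional hazards, but they describe status on a day, in the FAS, and not sustained withdrawal in the ITT population.
- A reader might infer that the pretest selects the main result. It does not. The stratified log-rank test is primary and keeps its type I error without proportional hazards; the Cox model is supportive and always reported.
- A reader might take 116 events per pair as a ceiling, or 70-85% as a property of the trial. The final count is not stated, and the miss rate depends on the assumed pattern.

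It is also fair that restricted means suffer from the same shortage of events. At 58 per arm, the simulated 95% CI half-width for the difference is about 0.9 days at Day 8, 1.8 at Day 15 and 3 at Day 31. The rows would describe the effect and its uncertainty, and would rarely settle it.

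**Conclusion.** The point holds as a reporting weakness in a supportive analysis. The restricted means and weighted log-rank tests depend on a test with little power at the event count the early stop implies. When that test does not reject, no between-arm estimate other than the hazard ratio is produced for the primary time-to-event endpoint.

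For moderate departures the test misses roughly 70-85% at about 110-143 events per pair. That range rests on the assumed patterns, an exponential control arm with median 8 days, no dropout before Day 31, an unstratified pairwise test, and an event count the SAP does not give. Under any of the moderate patterns tried, non-rejection is the more likely outcome. The validity of the primary comparison is not in question.

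**What to change.** In Section 7.6.3, remove the p < 0.05 condition for restricted means. In Table 14.2.1.1.2, remove the note that deletes the rows. Whatever the test shows, report restricted mean time per arm and, for each dose, the plitidepsin-minus-control difference in days with a 95% CI at Days 8, 15 and 31. Keep the treatment-by-log(time) test as descriptive and show it separately for each dose.

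Deal with the weighted log-rank tests at the same time: either name the weights, add rows and run them unconditionally as supportive, or drop them.

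SAP version 4.0 is dated 21 April 2023 and the database was locked on 26 April 2023. Any such output added after lock should be labelled post hoc. Section 1 of the addendum already allows additional tables.

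The cost is a few supportive rows, with wide intervals at this event count. No new data are needed.
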